2.3. Study Output Deliverable

This SAP will be used for Final Analysis CSR, Canada Health Authority Submission and Week 16 CSR. The data used by these deliverables are described as follows:

The Data Presentation Plan (DPS) will describe the details regarding which analyses and outputs are created for which purpose.

Outputs Deliverables	Analysis Coverage/Data to include/Cut point
Analysis for Canada Health Authority Submission	Data cut-off: 04MAY2020 Data extract: 05MAY2020 Outputs for efficacy and safety
Week 16 CSR	All available participants’ data in all age cohorts when all enrolled participants have finished all required Week 16 assessments or discontinued earlier from study permanently. Outputs for efficacy and safety
Final Analysis CSR	All datasets Outputs for efficacy and safety

2.4. Baseline Definition

Baseline: Baseline will be defined as the last non-missing assessment available prior to the first dose administration. Any unscheduled measurement performed before administration of study drug should also be used for determination of baseline across all the domains, as some tests may be repeated for confirmation.

3. PARTICIPANT AND TREATMENT INFORMATION

3.1. Demographics and Baseline Disease Characteristics

For all Safety Analysis Set participants, descriptive summary statistics will be provided for the following by age cohort, body weight and in the overall population, and listings by age cohort, country, site.

- Demographic and baseline characteristics: Age (year with decimal for month) at enrollment, Sex, Childbearing Potential for female participants, Race, Ethnicity, Weight (kg), Height (cm), and BMI (kg/m²).
 - Childbearing Potential and sexual activity for female participants at Screening (or eventually at re-screening) will be summarized together with the above demographics.
- Baseline disease characteristics:
 - From the 'PAH Etiology' eCRF module:
 - Etiology of PAH, association of PAH with congenital heart disease (CHD),
 - Date of first observed/assumed PAH symptoms (only for listing),
 - Time from first observed/assumed symptoms (days) (date of first observed/assumed PAH symptoms – date of screening + 1),
 - Date of PAH diagnosis (only for listing),
 - Time from PAH diagnosis (days) (date of PAH diagnosis – date of screening + 1).
 - From the 'WHO Functional Class' eCRF module:
 - Baseline WHO Functional Class.
 - From the 'Panama Functional Class for Pediatrics' eCRF module:
 - Baseline Panama FC.
 - From the 'Right Heart Catheterization' eCRF module:
 - Date of Diagnosis of right heart catheterization (RHC),
 - Mean pulmonary arterial pressure (mPAP[mmHg]),
 - Pulmonary arterial wedge pressure (PAWP[mmHg]) (or LAP or LVEDP),
 - Pulmonary vascular resistance index (PVRi[Wood units x m²]).
- Medical history (previous and ongoing clinically significant diseases) investigator original terms and preferred terms coded using the latest implemented MedDRA version dictionary will be listed.

3.2. Participant Recruitment, Disposition and Study Completion/Withdrawal Information

To describe participant disposition, the number of participants screened will be presented, and in addition, the following will be tabulated:

- Number (and % based on the Screened Analysis Set) of screening failures (all screened participants who were not enrolled)
 - Reasons for failure (from the “Enrollment” eCRF module)

- Number (and % based on the Screened Analysis Set) of enrolled participants (from the “Enrollment” eCRF module)
- Number (and % based on the Full Analysis Set) of dosed participants (with at least one record in the “Study Treatment Log” eCRF module)
- Number (and % based on the Safety Analysis Set) of participants who prematurely discontinued the study drug (from the “Premature Discontinuation of Study Treatment” and “Study Treatment Log eCRF modules)
 - Reasons for treatment discontinuation
- Number (and % based on the Safety Analysis Set) of participants who completed the study as per protocol (with completed EOS follow-up telephone call)
- Date and time of informed consent with the protocol version will be listed together with enrollment data (including reasons for not enrolling the participants) for all participants in the Screened Analysis Set.
- Unmet inclusion criteria and met exclusion criteria will be also listed for participants in the Screened Analysis Set.
- A participant listing of recruitment by country and center will be provided based on the Screened Analysis Set. In addition, for the same analysis set the number of participants recruited in each country and center (within country) will be tabulated.
- Study completion/Study premature discontinuations along with relevant reasons will also be listed for all Safety Analysis Set participants (“Study Discontinuation” eCRF modules).

For an individual participant, per protocol study completion is reached when the EOS follow-up telephone call is completed.

Participants who prematurely discontinued study treatment for any reason before completion of the last study visit phase will not be considered to have completed the study.

Check the details for prematurely discontinuation of study treatment in Protocol 5.1.9.

3.3. Previous and Concomitant Therapies and PAH-Specific Medications

All medications recorded in the ‘Previous/Concomitant Medication’ eCRF pages will be coded to preferred term using the latest version of the WHO Drug code and Anatomic Therapeutic Chemical class code dictionaries.

Previous medications are any medication/therapy with end date prior to the study drug start date.

Concomitant medications are defined as any medication/therapy with start date missing, or start date prior to, or on, or after the first study drug dose date but before last study drug dose, and with end date after the first study drug dose date, or end date missing.

In general, **concomitant medications** during study treatment include all medications taken whilst the participant is on study treatment, regardless of whether the start of intake is before the start of study drug. Concomitant medications include therefore concomitant medications at baseline and concomitant new medications.

Previous and concomitant medications (regardless of being PAH-specific or not) will be summarized by previous/concomitant medications class and preferred term and will be ordered according to decreasing frequency overall.

In addition, concomitant PAH-specific medications at baseline (i.e., used on the same day as the first dose of study drug but excluding the cases in which the medication ended on the day of first study drug dose), will be summarized. In this summary, PAH-specific medications will be presented by preferred term and PAH-specific medication subgroup name (as defined below). Also, the proportions of participants who received none, 1, 2, and 3 or more PAH-specific concomitant medications at baseline will be included.

The following preferred terms will define PAH-specific medications (except study treatment): “Ambrisentan”, “Bosentan” (including “Bosentan Monohydrate”), “Sitaxentan”, “Macitentan”, “Sildenafil” (including “Sildenafil Citrate”), “Tadalafil”, “Vardenafil”, “Udenafil”, “Riociguat”, “Iloprost”, “Epoprostenol”, “Treprostinil”, “Beraprost”.

All other medications will be classified as non-PAH-specific medication.

PAH-specific medications at baseline summary will be provided by preferred term with the following subgroup treatment categories:

- Treatment with Endothelin Receptor Agonist (ERA) monotherapy – identified by the following preferred terms (“Ambrisentan” OR “Bosentan” OR “Sitaxentan” OR “Macitentan”) AND NOT (“Sildenafil” OR “Tadalafil” OR “Vardenafil” OR “Udenafil”) AND NOT “Riociguat”.
- Treatment with phosphodiesterase type 5 (PDE-5) inhibitor monotherapy – identified by the following preferred terms (“Sildenafil” OR “Tadalafil” OR “Vardenafil” OR “Udenafil”) AND NOT (“Ambrisentan” OR “Bosentan” OR “Sitaxentan” OR “Macitentan”) AND NOT “Riociguat”.
- Treatment with combination of both ERAs and PDE-5 inhibitors – identified by the following preferred terms (“Ambrisentan” OR “Bosentan” OR “Sitaxentan” OR “Macitentan”) AND (“Sildenafil” OR “Tadalafil” OR “Vardenafil” OR “Udenafil”) AND NOT “Riociguat”.
- Treatment with prostacyclin/analogs (irrespective of treatment with ERAs or PDE-5 inhibitors or “Riociguat”) – identified by the following preferred terms “Iloprost” OR “Epoprostenol” OR “Treprostinil” OR “Beraprost” (it is expected to be rare as prostacyclin/analogs are not allowed to be co-administered according to the study protocol).

- Treatment with soluble guanylate cyclase stimulator (irrespective of ERAs or PDE-5 inhibitors or prostacyclin/analogs) – identified by the preferred term “Riociguat”.

All medications/therapies will be listed together. A different flag will indicate if the medication is previous or concomitant respectively. Additionally, forbidden and PAH-specific medications will be flagged.

All summaries will be provided by age cohort and body weight group.

All PAH-related non-pharmacological interventions recorded on the dedicated eCRF form will be listed.

If missing end date or the medications ended on or after first dose date of the study drug, the medication will be classified as concomitant medication. If both start date and end date are missing, then this medication will be considered as both previous and concomitant medications.

3.4. Protocol Deviations

Major protocol deviations and COVID-19 related deviations will be reported in the database.

A listing of participants with major protocol deviations will be provided as well as a listing with any COVID-19 related deviations, including all available details about these deviations.

Between visits, compliance is expected to be between 80% and 120%. Compliance values outside of this range will be considered as protocol deviations (see details in Protocol 5.1.7.2.).

3.5. Extent of Exposure and Compliance

Exposure data are taken from the “Study Treatment Log” eCRF module.

All data recorded will be listed, together with treatment exposure duration (weeks) derived as defined below. The listing will also display the body weight at baseline, as this parameter triggers the starting dose.

Treatment duration (days) is defined as date of last intake of study drug minus date of first intake of study drug plus 1. It includes therefore any possible treatment interruption.

The treatment exposure duration (days) takes account of periods of drug interruption. To calculate the treatment exposure duration per participant, the number of days the participant took no study treatment is subtracted from the treatment duration defined above.

The treatment exposure duration (weeks) will be then calculated by dividing the treatment exposure duration (days) by 7.

Treatment duration or treatment exposure duration (weeks) will be summarized as categorical data. The duration categories will be cumulative for <=4 weeks, <=8 weeks, <=12 weeks, <=16 weeks, <=52 weeks.

Study treatment compliance is based on study treatment accountability. Study treatment compliance will be calculated by site personnel at visits as indicated in the assessment schedule using the below formula and entered in the eCRF:

$$\text{Compliance} = 100 \times (\text{number of tablets dispensed} - \text{number of tablets returned}) / \text{Total number of tablets that should have been taken during the period}^*$$

*The period is defined as the number of days of treatment from the date of dispensation / start of study treatment until the next accountability visit. The number of tablets that should have been taken should be calculated on a participant basis, based on the investigator's prescription.

Study treatment compliance, reason of non-compliance will be summarized at each timepoint. Details of study treatment dispensing and accountability will be listed for each participant.

3.6. Individual maximum tolerated dose(iMTD)

The iMTD is defined as the last dose received before the Week 12 visit (for participants who prematurely discontinued study drug) or the dose received on the day of the Week 12 visit (for participants who completed the 12-week up-titration period).

For each iMTD, the number and percentage of participants who reached this dose will be summarized by age cohort and body weight group categories (≥ 9 to < 25 kg, ≥ 25 to < 50 kg, ≥ 50 kg) at baseline.

The iMTD reached for each participant will be indicated in the study drug administration listing.

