#### 5.1.4 Study drug starting dose and up-titration

At the Baseline/Enrollment visit, based on the participant's body weight, the body weight category, starting dose, and up-titration scheme will be determined.

Study medication administration will start in the evening of Day 1 and continue thereafter with b.i.d. dosing, i.e., in the morning and in the evening. During the up-titration period of 12 weeks, it is recommended that the doses are increased weekly in increments equal to the starting dose until the participants reach their iMTD or until a maximum dose corresponding to their baseline body weight category is achieved.

To improve tolerability, it is recommended that the study drug, selexipag, is taken with food and, at the beginning of each up-titration phase, that the first increased dose is taken in the evening. The maximum dose allowed to be administered will be 8-fold the corresponding starting dose:

- Body weight category  $\geq 50$  kg: starting dose of 200  $\mu\text{g}$  titrated up to the iMTD of 1,600  $\mu\text{g}$  b.i.d. Participants in this category will receive 200  $\mu\text{g}$  tablets only [Table 1].
- Body weight category  $\geq 25$  to  $< 50$  kg: starting dose of 150  $\mu\text{g}$  titrated up to the iMTD of 1,200  $\mu\text{g}$  b.i.d. Participants in this category will receive a combination of 50  $\mu\text{g}$  mini-tablets and 200  $\mu\text{g}$  tablets [Table 2].
- Body weight category  $\geq 9$  to  $< 25$  kg: starting dose of 100  $\mu\text{g}$  titrated up to the iMTD of 800  $\mu\text{g}$  b.i.d. Participants in this category will receive either a combination of 50  $\mu\text{g}$  mini-tablets and 200  $\mu\text{g}$  tablets, or 50  $\mu\text{g}$  mini-tablets only, if requested by the investigator [Table 3].

Two study-treatment supply options are available:

Option 1 will supply participants able to swallow tablets whole with water with a combination of 200  $\mu\text{g}$  tablets and 50  $\mu\text{g}$  mini-tablets to minimize the overall number of tablets per intake and will be provided via IRT by default, and

Option 2 will supply participants with 50  $\mu\text{g}$  mini-tablets only upon request by investigator, if study treatment is to be taken with soft food or dispersed in apple/ orange juice.

The up-titration will be agreed upon during scheduled telephone calls or visits.

At Week 12 the iMTD for each participant will be determined. This dose should be kept unchanged until Week 16.

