The body weight category, starting dose, and up-titration scheme determined at Baseline/Enrollment will be kept unchanged until Week 16. After Week 16, if the body weight category of the participant changes, study drug can be up-titrated further or down-titrated to the corresponding dose level of the next body weight category, as deemed appropriate by the investigator (if dose levels overlap between body weight categories, the dose level may also remain stable).

In addition, irrespective of whether the body weight category changes or not, after Week 16 the investigators will be allowed to change the participant's study medication dose further if needed (up to the maximum allowed dose based on body weight category).

If a participant has tolerability issues and experiences adverse reactions reflecting the mode of action for selexipag [see Section 5.1.10], the dose can remain the same without further up-titration (pause in up-titration). Up-titration can be resumed after the pause, or the dose can be reduced to the previous dose level. The decision to pause up-titration, to up-titrate or down-titrate study drug, or to permanently discontinue study drug treatment will be based on the investigator's medical judgment [see Section 5.1.10].

If a dose of selexipag is missed, participants should take a dose as soon as possible unless the next dose is within the next 6 h. During the up-titration period, the investigator / site staff must ensure that PK samples are collected after 3 days at the same dose and using the same mode of administration.

At any time during study treatment, study drug interruptions (eg, missed doses for any reason) of 3 days or more will require a new up-titration according to the scheme from Day 1.

All selexipag dose changes and reasons for dose interruptions must be documented in the eCRF.

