#### ~~10.3.4~~ Exploratory pharmacokinetic / pharmacodynamic analysis

The population PK/PD model will be built based on individual predictions of steady-state exposure for iMTD based on the final population PK models for both selexipag and ACT-333679. More details on PK and PD analyses will be in the modeling data analysis plan.

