2.2. Study Analysis Periods

For each dosed participant, the screening, treatment and follow-up phases of the study will be structured as following:

Table 3: Study periods definition

Period	Period Start	Period End
Screening	Starts with the signature of the informed consent form (ICF), may be as early as Day -42	Prior to the administration of the first study treatment dose
Treatment		
Up-Titration	the first dose of study treatment	the participant reaches their iMTD (iMTD for each participant is determined at Week 12, or EOT + 3 days in case of premature treatment discontinuation before Week 12)
Maintenance after Week 12 to 16 (continue treatment at same dose)	Day of Up-Titration end plus 1.	Up to Week 16 or EOT + 3 days in case of premature treatment discontinuation before Week 16

Period	Period Start	Period End
Maintenance after Week 16	Day of Week 16 visit plus 1	EOT (up to 5 years after last participant, first visit)
EOT visit	This visit should be conducted within 1 week of the last dose of study treatment. The participant will then enter the Safety follow-up period.	
Safety follow-up	Day after EOT	EOS - Day of Safety follow-up Phone call (about 30 days after last dose)

In case a participant drops out during a treatment period, the participant will have a Follow-Up period after the last applicable treatment period only if a Follow-Up visit was performed.

Each of these analysis periods is associated with a treatment. Treatments for the Screening and Follow-Up periods are defined as ‘None (screening/follow-up)’, respectively.

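### The iMTD is read off the Week 12 visit day, so a child restarted from about Week 7 after an interruption can be given an iMTD below a dose already taken

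*SAP*

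**What the plan says.** - **Definition.** SAP 3.6 gives two cases. For early stoppers: "The iMTD is defined as the last dose received before the Week 12 visit (for participants who prematurely discontinued study drug". For everyone else: "the dose received on the day of the Week 12 visit (for participants who completed the 12-week up-titration period". Protocol 10.3.5 and 10.3.7 say the same.
- **Titration.** In Protocol 5.1.4, "it is recommended that the doses are increased weekly in increments equal to the starting dose", and "The maximum dose allowed to be administered will be 8-fold the corresponding starting dose". Tables 1 to 3 lay this out as eight levels. Their footnote describes a different quantity: the top dose the child tolerated up to Week 12.
- **Restart.** The same section says that interruptions "of 3 days or more will require a new up-titration according to the scheme from Day 1", whenever they occur and whatever the reason.
- **After Week 12.** Of the dose fixed at Week 12, Section 5.1.4 says: "This dose should be kept unchanged until Week 16". SAP 2.2, Table 3, names the following period "Maintenance after Week 12 to 16 (continue treatment at same dose".
- **Uses.** SAP 3.6 tabulates the iMTD by age cohort and weight group and lists it. Protocol 10.3.5, 10.3.6 and 10.3.7 call for analyses by iMTD dose group. Protocol 10.3.4 builds the PK/PD model on "individual predictions of steady-state exposure for iMTD". An exploratory objective (Protocol 2.3, SAP 1.1) relates exposure at the iMTD to 6MWD.

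**The concern.** The visit-day definition works only if titration is over by Week 12. After a late restart it is not, and the dose that day depends on how many weeks have passed since the restart. Such a child would enter the iMTD table as tolerating only a low dose, even if the top level had been taken earlier.

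The definition also has two smaller gaps. A child interrupted on the visit day has no dose to record. If a weekly step falls on that day, the morning and evening doses differ, and nothing says which one counts.

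Cohorts are small: one wrong value is 1/20 = 5% to 1/15 = 7% of a cohort. For adverse events, any re-titration after Week 12 falls in a period labelled as constant dose, although Protocol 5.1.10 notes that mode-of-action reactions cluster in the titration phase.

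**Working it through.** **Inputs.** Weekly steps taken in the evening, eight levels (Protocol 5.1.4, Tables 1 to 3). Week 12 visit with a window of 3 days either side (Table 4). Week k is taken as Day 7k + 1, so Week 12 is Day 85. Assumed: evening restart, on-schedule steps, no tolerability pauses.

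**Formula.** The level t days after an evening start or restart is L(t) = min(8, floor(t/7) + 1).

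**Reproducing the plan.** From Day 1, level 8 begins 49 days later, on Day 50 in the evening, which is Week 7 p.m. The levels are 200 to 1,600, 150 to 1,200 and 100 to 800 µg by weight category. Both match Tables 1 to 3.

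**Restart on Day R after a gap of g days.** Level held before the gap: L(R − g − 1). Week 12 morning: L(85 − R − 0.5). Week 12 evening: L(85 − R). For example, Week 10 is R = 71. With g = 3 the earlier level is L(67) = 8; the morning level is L(13.5) = 2 and the evening level L(14) = 3.

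| Restart (3-day gap) | Level before | Week 12 morning / evening | Percent of earlier level |
|---|---|---|---|
| Week 5 | 5 | 7 / 8 | 140 / 160 |
| Week 6 | 6 | 6 / 7 | 100 / 117 |
| Week 7 | 7 | 5 / 6 | 71 / 86 |
| Week 8 | 8 | 4 / 5 | 50 / 63 |
| Week 9 | 8 | 3 / 4 | 38 / 50 |
| Week 10 | 8 | 2 / 3 | 25 / 38 |
| Week 11 | 8 | 1 / 2 | 13 / 25 |

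**Onset.** Day by day, the Week 12 dose first drops below the earlier dose for a restart on Day 46 (Week 6.4) after a 3-day gap. After a 7- or 14-day gap this is Day 50 (Week 7). The morning dose first falls to half or less for a restart on Day 57 (Week 8), or Day 64 (Week 9) after a 14-day gap.

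**Lower tolerated levels.** A child whose tolerated level is T regains it by the Week 12 morning if restarted no later than Day 84 − 7(T − 1). For T = 4 that is Day 63, so loss begins at about Week 9. For T = 8 it is Day 35 (Day 32 to 38 across the visit window).

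**PK/PD illustration.** 6MWD is measured at Week 16 (Day 113). A Week 10 restart that continues weekly is then at L(113 − 71 − 0.5) = level 6 in the morning, against a recorded morning iMTD of level 2. Under the dose proportionality assumed in Protocol 3.2, the assigned exposure would be 2/6, or one third, of the actual exposure. If the dose were held after Week 12, this mismatch would not arise; the text supports either reading.

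**Adverse event period.** Level 8 is regained 49 days after restart: Day 106 (Week 15) for a Week 8 restart and Day 113 (Week 16) for Week 9. Continued re-titration from Week 9 or later would therefore fill the whole Week 12 to 16 period.

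**The case against.** **The impact is narrow.** Within the SAP the iMTD feeds one table and a listing; SAP 4 and 5 analyse by age cohort and weight group. SAP 1 leaves PK and PK/PD modelling to separate plans, which may already use actual doses. This stands. A reader might infer that the exposure-response results will be distorted, but without the modelling plan that cannot be shown. It can be said only that Protocol 10.3.4 names exposure at the iMTD as the basis.

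**Week 5 is not the threshold.** Full titration takes seven weeks, so a reader might infer that any restart after about Week 5 gives an iMTD far below the tolerated dose. The schedule does not support this. Week 5 is only the last point from which level 8 can be regained. A child restarted then had reached level 5 at most and is on level 7 or 8 at Week 12. Level 8 is not reachable before Week 7 p.m.

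**A lower dose may be right.** Protocol 5.1.8 includes adverse events among the reasons for interruption. For those children a low Week 12 dose may reflect tolerability, so the reason should be shown.

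**The records allow reconstruction.** Interruptions to Week 16 are recorded and treatment log data are listed, so a reader could trace each case. That limits the harm but does not correct the summary table.

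**General rule and exception.** The instruction to hold the Week 12 dose can be read as general, with restart as the exception. That is plausible, but the text does not say so.

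**The Week 12 split is prespecified.** Protocol 10.3.5.1 itself divides adverse events at Week 12. The split can stay; what needs correcting is the implication of a constant dose.

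**Conclusion.** The gap is real and worth closing. As written, the rule can record an iMTD below a dose already taken for restarts from about Week 6.5 to 7. The value is half or less of the earlier dose from about Week 8, and 13% to 25% of it at Week 11 for a child who had been on level 8. Children with lower tolerated levels are affected only by later restarts.

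The figures rest on on-schedule weekly steps, an evening restart and no pauses. Weekly steps are only recommended, and slower re-titration would lower the level regained by Week 12. The documents give no interruption rate, so no count of affected children is supportable.

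A reader might infer that confirmation of the starting dose is at risk. It is not, to any material degree: the primary endpoint is model-based exposure, and PK is assumed dose-proportional.

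**What to change.** - **SAP 3.6.** Flag children whose re-titration is incomplete, or who are interrupted, on the Week 12 visit day as *iMTD not determined at Week 12 (re-titrating)*. Give them their own row in the iMTD table, with the highest level taken before the interruption and the reason for it. State whether the morning or evening dose counts on the visit day.
- **Modeling data analysis plan.** For these children, use the actual dose at the time of each assessment.
- **SAP Table 3.** Flag adverse events that start during a re-titration after Week 12, so that they are not read as events at a constant dose.
- **Protocol.** Reconcile the Section 5.1.4 passages on restarting titration and on holding the Week 12 dose to Week 16. Reconcile the visit-day definition with the footnote to Tables 1 to 3. No dosing rule is proposed here.

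The cost is low. Protocol 5.1.8 already requires every interruption to Week 16 to be recorded, and SAP 3.5 draws on the Study Treatment Log, so no new data are needed. The downside is a few children without a Week 12 iMTD.
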